2.5 Safety endpoints

Safety endpoints:

- Drug Administration:
 - Relative dose intensity: $RDI = \left(\frac{DDI}{SDI} \right) \times 100$
 - DDI = Delivered dose intensity
 - SDI = Standard dose intensity
 - Duration of treatment: It is defined as the period of time from treatment initiation to the end of treatment.

- Duration of follow-up: It is defined as the period of time from treatment initiation to the end of study follow-up visit date or the latest date available.
- Percentage of patients with dose reduction: It is defined as the proportion of participants with dose reduction relative to the number of patients in the analysis set. The reasons for dose reduction will be also reported.
- Percentage of patients with dose delays: It is defined as the proportion of participants with dose delays or temporary interruption relative to the number of patients in the analysis set. The reasons for dose delays will be also reported.
- Percentage of patients discontinued: It is defined as the proportion of participants discontinued to any cause relative to the number of patients in the analysis set. The reasons for study discontinuation will be also reported.

- Adverse events:

The incidence of AEs, TEAEs, TEAEs grade ≥ 3 , related TEAEs, AESI, SAEs, TEAEs leading to dose reduction, dose delay, permanent discontinuation or death will be summarized according to the Medical Dictionary for Regulatory Activities (MedDRA) preferred term and graded using the NCI-CTCAE v.5. Other safety parameters such laboratory parameters, the extent of exposure to study medication, concomitant medications, vital signs, physical examination, reason for treatment reductions, delays, discontinuations, and reason for follow-up discontinuations will be summarized.

- Laboratory parameters:

- Hematology parameters
- Biochemistry parameters

- Additional safety parameters:

- Concomitant medications
- Vital signs
- Physical examination
- ECOG performance status

3 ANALYSIS SETS

Modified intention to treat (mITT) set

All randomly assigned patients that accomplish major selection criteria (Central Ki67 $\geq 10\%$), with ≥ 14 days of treatment*, and the central Ki67 evaluated at baseline and at most on the day after the completion of treatment. Subjects will be analyzed according to treatment allocated. The mITT set will be used for primary and secondary efficacy analysis.

*One day of deviation from the 15 days of treatment indicated for the main objective will be accepted.

Intention-to-treat (ITT) analysis set

All patients randomized. Subjects will be analyzed according to treatment allocated. The ITT set will be used for supportive efficacy analyses.

Per protocol analysis (PP) set

All randomly assigned patients that accomplish major selection criteria, with Ki67 evaluable values at baseline and after the treatment, with a minimum exposure to the drugs assigned in the randomized arm, and without major protocol deviations. Criteria for determining the "per protocol" group assignment would be established by the Steering Committee before the statistical analysis begins. Subjects will be analyzed according to treatment received. The PP set will be used for supportive efficacy analyses. This analysis will only occur if this set differs by $\geq 10\%$ from the mITT set.

Safety analysis set

Includes all patients who received at least one dose of the study drug. Subjects will be analyzed according to treatment received. The safety set will be used for analyses of safety endpoints.

4 STATISTICAL METHODS

4.1 General Methodology

The statistical analysis will be conducted following the principles as specified in International Conference on Harmonization (ICH) Topic E9 (CPMP/ICH/363/96). The significance level will be $\alpha=0.05$ for all tests. As an exploratory study, multiple testing without adjustment of the significance level is considered acceptable.

Definition of baseline: For each safety or efficacy parameter, the last valid assessment made before first study drug administration will be used as the baseline for all analyses of that safety or efficacy parameter unless otherwise specified.

Continuous data will be summarized in terms of the number of observations, mean, standard deviation (SD), median, minimum, maximum, and first and third quartiles, unless otherwise stated. Where data are collected over time, both the observed data and change from baseline will be summarized at each time point.

The minimum and maximum will be reported to the same number of decimal places as the raw data recorded in the database. The mean, median, and first and third quartiles will be reported to one more decimal place than the raw data recorded in the database. The SD will be reported to two more decimal places than the raw data recorded in the database. In general, the maximum number of decimal places reported shall be four for any summary statistic.

Categorical data will be summarized in terms of the number of subjects providing data at the relevant time point (n), frequency counts and percentages. Changes from baseline in categorical data will be summarized using shift tables where appropriate.

Percentages will be presented to one decimal place. A percentage of 100% will be reported as 100.0%. Unless otherwise stated, percentages will be calculated using n as the denominator. If sample sizes are small, the data displays will show the percentages, but any textual report (e.g., clinical study report) will describe frequencies only.

P-values greater than or equal to 0.001, in general, will be presented to three decimal places. P-values less than 0.001 will be presented as "<.001".

Confidence intervals will be presented to one more decimal place than the raw data. A two-sided significance level of 95% will be used for confidence intervals.

For binary endpoints, the 95% confidence intervals (CIs) will be constructed based on Clopper-Pearson.

The Kaplan-Meier method will be used to estimate the time to event function, the median of time to event, minimum, maximum and the 95% confidence interval of the same will be calculated. These confidence intervals will be calculated based on the Greenwood method. Number of patients included in the analysis and total number of events will be shown.

All scores and change from baseline will be summarized in terms of the number of observations, mean, standard deviation, median, range and interquartile range.

All report outputs will be produced using SAS® version 9.4 version or posterior in a secure and validated environment under SAS Enterprise Guide v8.3 or later user interface. All report outputs will be provided to the Sponsor in rtf format.

4.2 Subject Disposition

Descriptive statistics will be provided for the following:

- Overall number of subjects in the screening set, the number of patients eligible to participate in the study, and number of screening failures.
- Number and percent of subjects in each of the analysis sets.
- Number and percent of subjects excluded from each of the analysis sets along with reason for exclusion.
- Listing of subjects excluded from each of the analysis sets along with reason for exclusion.
- Listing of protocol deviations.

- Number and percent of subjects from End of Treatment.
- Number and percent of subjects form End of Study with reasons.

4.3 Baseline Characteristics

Descriptive statistics will be provided for the following baseline characteristics:

- **Demographic data:** sex, age, ethnicity, country; for women, pregnancy test, contraception methods and/or menopausal status; and for men, contraception endpoints;
- **Medical history:** habits (smoking, alcohol and drugs consumption), significant diseases, surgeries, other cancers, previous therapies and procedures; Breast cancer history: study tumor characteristics, previous treatment for breast cancer (radiotherapy and/or antineoplastic);
- **General assessment at baseline:** physical examination and vital signs endpoints; ECOG performance status, and 12-Lead ECG; Molecular biomarkers, Coagulation endpoints, Haematology and Biochemistry parameters; Tumor assessment before the study treatment, including tumor sample and radiologic imaging; and
- **Concomitant medication** prior to screening visit.

All parameters will be described according to their characteristics, as follow:

- **Categorical variables** will be summarized using number, frequencies and percentages.
- **Continuous variables** will be summarized using measures of central tendency and dispersion: mean, standard deviation, median, 25% and 75% percentiles (Q1 and Q3) and extreme values (minimum and maximum).

4.4 Efficacy Analysis

Primary efficacy analysis will be reported for either mITT, ITT and PP sets.

Second efficacy analysis will be reported for mITT set.

4.4.1 Primary Efficacy Endpoint

The change in tumor cell proliferation as measured by Ki67 expression between baseline and the post-treatment tumor biopsy samples by central assessment.

The primary analysis will be done for the mITT analysis set. We only will analyse observed valid cases (observed-cases method).

The global null hypothesis is that the giredestrant (GDC-9545) does not differ from tamoxifen treatment group in the mean percentage of absolute difference in Ki67 between baseline score and after the treatment. The alternative hypothesis is that the giredestrant (GDC-9545) differs from the tamoxifent treatment group.

The test of the null hypothesis is based on a two-sided Wilcoxon unpaired test set at 0.05 alpha level. It includes treatment as a factor. The response variable is the absolute difference in Ki67 score after the treatment. We propose declaring the superiority of giredestrant (GDC-9545) therapy if shown to be superior in this analysis.

We will estimate the 95% confidence intervals (CI) for the mean and median of absolute difference between baseline and the post treatment evaluation in each study arm. The 95% confidence intervals (CI) for the mean and median difference between treatments are estimated by the T-Test and Hodges–Lehmann estimator, respectively.

Individual baseline and post-treatment Ki67 scores will be summarized with dot plots linking with a line the observations of the same patient. Absolute and relative change between baseline and post-treatment will be summarized with waterfall and bar plots.

4.4.1.1 Missing data imputation methods

The values of Ki67 could be missing for patients without valid analytic values or withdrawal. Missing values for primary endpoint will be managed with three methods:

- a) Observed case imputation: Only observed valid cases are analyzed.
- b) Last observation carried forward: Missing value are replaced by the last value observed before.
- c) The standard multiple imputation performed in three steps: (1) the imputation of non-monotone missing data using MCMC. A total of 10 complete datasets are generated within this step; (2) the imputation of monotone missing data with regression models; (3) the calculation of endpoint estimates, standard errors and p-values for each dataset; and (4) the combination of all dataset results by Rubin's rules.

4.4.1.2 Supportive analyses for primary efficacy endpoint

The primary endpoint analysis will be repeated for the PP and ITT set as described in the previous section. For ITT analysis the missing values for Ki67 after the treatment are imputed with baseline Ki67 scores based on the last observation carried forward principle (0 score in absolute difference of Ki67). For PP analysis only observed valid cases will be analyzed.

Additionally, the following supportive analyses will be performed (Table 6. Planned analyses for the primary endpoint.):

- a) The Ki67 score after two weeks of treatment will be adjusted by baseline Ki67 scores. The analysis will be done for the mITT, ITT and PP analysis set (as appropriate). We only will analyze observed valid cases for mITT and PP analysis set. Alternatively, the missing management method for ITT analysis will be the multiple imputation.

The test of the null hypothesis is based on a linear regression model which includes treatment as a factor and baseline Ki67 score as covariate. The response variable is the Ki67 score after the treatment. The transformed values of the Ki67 score are assumed to be a linear function of the treatment as:

$$Y = \beta_0 + \beta_1 X_1 + \beta_2 X_2$$

where

Y = The Ki67 score after the treatment,

β_0 denotes intercept,

β_1 denotes the treatment effect,

X1 refers to the treatment groups (Giredestrant (GDC-9545) and tamoxifen),

β_2 denotes the Ki67 baseline score effect,

X2 refers to the Ki67 baseline score.

The parameterization method is based on a reference group (tamoxifen). The p-values and 95% CI are estimated by the Wald method. The 95% CI will be also reported back transformed.

- b) The relative percentage of change between baseline and the post treatment evaluation in each patient will be calculated using the baseline and post-treatment scores divided by baseline scores per 100. The 95% CI for the arithmetic and geometric mean in each arm will be estimated with T-Test.

The geometric mean will be estimated using the log values for the relative percentage of change. The log-transformation is designed for non-negative values, so we will add a constant to the individual values of relative percentage change before applying the transformation. The 95% CI for the geometric mean will be reported back transformed using the anti-log scale and subtracting the constant. The analysis will be done for the mITT, ITT and PP analysis set (as appropriate). We only will analyze observed valid cases for mITT and PP analysis set. Alternatively, the missing management method for ITT analysis will be the multiple imputation.

Table 1. Planned analyses for the primary endpoint

ID	Set	Analysis sets	Main estimate and (Imputation Method)	Type of analysis
1	mITT	Patients excluded: -Central Ki67 < 10% or not evaluable at baseline. -<14 days of treatment. -Without the Ki67 central evaluation at baseline and after at most on the day after the completion of treatment.	Central Ki67 score Difference between baseline and post treatment evaluation. (Observed case)	Primary -Willcoxon unpaired -95% CI T-test -95% CI HL
2	ITT	All patients randomized regardless of IEs are included (Treatment policy strategy).	Central Ki67 score Difference between baseline and post treatment evaluation. (Last observation carried forward)	Supportive -Willcoxon unpaired -95% CI T-test -95% CI HL
3	PP	Patients excluded: -Central Ki67 < 10% or not evaluable at baseline. -Without the Ki67 central evaluation after the treatment -Patients with other major deviations in accordance steering committee.	Central Ki67 score Difference between baseline and post treatment evaluation. (Observed case)	Supportive -Willcoxon unpaired -95% CI T-test -95% CI HL
4	mITT	See above ID nr. 1	Central Ki67 score Ki67 score after the treatment adjusted by baseline score. -Box-cox transformation (Observed case)	Supportive -Linear regression (Wald test) adjusted by baseline scores
5	ITT	See above ID nr. 2	Central Ki67 score Ki67 score after the treatment adjusted by baseline score. -Box-cox transformation (Multiple imputation)	Supportive -Linear regression (Wald test) adjusted by baseline scores
6	PP	See above ID nr. 3	Central Ki67 score Ki67 score after the treatment adjusted by baseline score. -Box-cox transformation (Observed case)	Supportive -Linear regression (Wald test) adjusted by baseline scores
7	mITT	See above ID nr. 1	Central Ki67 score % of change between baseline and post treatment evaluation. (Observed case)	Supportive -95% CI for arithmetic and geometric means in each arm
8	ITT	See above ID nr. 2	Central Ki67 score % of change between baseline and post treatment evaluation. (Multiple imputation)	Supportive -95% CI for arithmetic and geometric means in each arm
9	PP	See above ID nr. 3	Central Ki67 score % of change between baseline and post treatment evaluation. (Observed case)	Supportive -95% CI for arithmetic and geometric means in each arm

4.4.2 Secondary Endpoints and Subgroup Analysis

The secondary efficacy endpoints will be done for the mITT analysis set. We only will analyze observed valid cases.

For quantitative measures (Ki67, ER, PR, and other molecular markers) the mean, median, geometric mean, standard deviation, interquartile range, and range will be reported as appropriate per study arm and visit. Summary statistics for the absolute and relative change between baseline and post-treatment will be also reported.

Individual baseline and post-treatment scores in quantitative measures will be summarized with dot plots linking with a line the observations of the same patient. Absolute and relative change between baseline and post-treatment will be summarized with waterfall and bar plots.

The difference between baseline and post-treatment evaluation will be compared in each arm with Wilcoxon paired test. We will estimate the 95% confidence intervals (CI) for the mean and median.

The difference between study arms at baseline and after the treatment will be compared with Wilcoxon unpaired test. We will estimate the 95% confidence intervals (CI) for the mean and median difference between treatments with T-Test and Hodges–Lehmann estimator, respectively. The comparison of quantitative score after two weeks of treatment in each arm will be adjusted by baseline scores based on linear regression.

For qualitative measures (CCCA [Ki67 \leq 2.7%] after the treatment) we will calculate the number and proportion of patient achieving the cut-off criterion. We will estimate the proportions with the 95% Clopper-Pearson confidence intervals. The between arms comparison will be conducted with logistic regression models. Factor estimates, odds ratios, corresponding 95% confidence intervals, and p-value will be presented. P-values and 95% confidence intervals will be based on Wald test.

The comparison of primary and secondary endpoints between patient and molecular characteristics will be conducted if considered appropriate. The quantitative endpoints will be analyzed with linear regression based on Wald test. The binary endpoints will be analyzed with logistic regression models. Factor estimates, odds ratios, corresponding 95% confidence intervals, and p-value for applicable test statistics will be presented. P-values and 95% confidence intervals will be based on Wald test.

For all secondary analyses, we will use two-sided p-values with $\alpha \leq 0.05$ level of significance and 95% confidence intervals.

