1.5.1 Clinical overview of giredestrant (GDC-9545)

The study NCT03916744 was a phase I, open-label, multicenter trial of giredestrant (GDC-9545) to evaluate pharmacodynamics, pharmacokinetics, safety, and biologic activity of the drug in postmenopausal women with stage I-III operable ER-positive/HER2-negative untreated BC. 75 patients were assigned to 15 (±2) days of treatment with giredestrant (GDC-9545) orally once daily (PO QD) at a dose of either 10, 30, or 100 mg followed by surgery. Tumor tissue samples were collected at baseline and at the end of treatment. The primary objective of the study was to measure changes in the Ki67 between pre- and post-treatment samples. Preliminary results from 47 evaluated patients shown that 77% were classified as Luminal A and 23% Luminal B at baseline. Giredestrant (GDC-9545) treatment was well tolerated, no grade 4 or 5 adverse events (AEs) were reported and single serious grade 3 that appeared were unrelated to giredestrant (GDC-9545). In addition, it was biologically active at all doses. The post-treatment Ki67 reduction was 80% at 10 mg, 76% at 30mg and 80% at 100mg. Notably, 51% of tumors exhibited complete

cell cycle arrest (CCCA, Ki67 $\leq 2.7\%$) and the mean post-treatment proportional reductions of ER and PgR (progesterone receptor) H-scores were 71% (95% CI: 67–75) and 60% (95% CI: 51–70), respectively (Moore et al., 2021).

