The phase II coopERA trial (NCT04436744) was a two arm, open-label, multicenter trial aimed at evaluating the efficacy, safety and pharmacokinetics of giredestrant (GDC-9545) plus palbociclib compared with anastrozole plus palbociclib in postmenopausal women with untreated ER-positive/HER2-negative EBC. 221 patients with baseline Ki67 score $\geq 5\%$ were randomized 1:1 to receive 14 days of anastrozole (1 mg, PO QD) or giredestrant (GDC-9545) (30 mg, PO QD) (window-of-opportunity phase, WoO) followed by 16 weeks (four 28-days cycles) of additional neoadjuvant palbociclib (125 mg, PO, D1-21) treatment prior to surgery. The primary objective of the study was to measure tumoral Ki67 changed between baseline and post-WoO samples. In ESMO Breast 2021, preliminary results were shown for 83/202 planned patients. Two-week relative Ki67 reduction was significantly greater with giredestrant (GDC-9545) than anastrozole (80% versus 67%, respectively) and a consistent Ki67 suppression was observed in patients with baseline Ki67 $\geq 20\%$ (giredestrant (GDC-9545): 83% reduction; anastrozole: 71%) or $< 20\%$ (65% vs 24%). After 14 days of treatment, 25% of tumors exhibited complete cell cycle arrest (secondary objective) with giredestrant (GDC-9545) versus 5% with anastrozole. Patients treated with giredestrant (GDC-9545) had fewer AEs than anastrozole.

Table 2 summarizes ongoing clinical trials with giredestrant (GDC-9545) for the treatment of early or advanced hormonal receptor-positive BC. In addition, giredestrant (GDC-9545) is also being studied in the treatment of ER-positive/HER2-positive BC.

Table 2. Ongoing clinical trials with giredestrant (GDC-9545) in BC.

Clinical Trial	Phase	Study
NCT03916744	I	A Phase I, Multicenter, Open-Label Preoperative, Short-Term Window Study of GDC-9545 in Postmenopausal Women With Stage I-III Operable, Estrogen Receptor-Positive Breast Cancer
NCT03332797	Ib/II	Multicenter, Open-Label, Dose Escalation, Dose Expansion Study Evaluating the Safety, Pharmacokinetics, and Activity of GDC-9545 Alone or in Combination With Palbociclib and/or LHRH Agonist in Patients With Locally Advanced or Metastatic Estrogen Receptor-Positive Breast Cancer
NCT04802759	Ib/II	Open-Label, Multicenter, Randomized Umbrella Study Evaluating the Efficacy and Safety of Multiple Treatment Combinations in Patients With Breast Cancer (MORPHEUS-Breast Cancer)

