2.4 Endpoints definitions

Primary endpoint:

Changes in tumor cell proliferation as measured by Ki67 expression between baseline and post-treatment tumor biopsy samples by central assessment in patients with centrally confirmed Ki67 $\geq 10\%$ (Arm A vs Arm B).

Secondary endpoints:

- CCCA in all arms, defined as the percentage of participants with centrally assessed Ki67 scores $\leq 2.7\%$ stained nuclei upon treatment (post-treatment sample).
- Changes in markers (such as ER and PgR levels) and molecular profiling using HTG (PAM-like molecular test).
- Incidence and severity of adverse events (AEs), with severity determined in accordance with NCI-CTCAE v.5.0.

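### CCCA is compared between arms by Wald logistic regression with no fallback for a zero cell; if no tamoxifen patient reaches CCCA, the p-value is about 1 whatever giredestrant achieves

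*SAP*

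**What the plan says.** CCCA is the first-listed secondary endpoint (SAP 2.4). On its analysis, SAP 4.4.2 says:

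- Analysis set: "The secondary efficacy endpoints will be done for the mITT analysis set", observed cases only.
- Between-arm test: "The between arms comparison will be conducted with logistic regression models".
- Inference: "P-values and 95% confidence intervals will be based on Wald test".

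Secondary tests are two-sided at 0.05. Protocol 8.7 specifies the same method, and SAP section 6 records no change from the protocol. Neither document provides for a zero cell: there is no exact, score or likelihood-ratio test, no profile limits and no penalised fit. The only exact method is in SAP 4.1: "For binary endpoints, the 95% confidence intervals (CIs) will be constructed based on Clopper-Pearson". SAP 4.4.2 applies it to each arm's proportion, so it is not a between-arm comparison.

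No tamoxifen CCCA rate is given. The closest randomised figure is in Protocol 1.5.1, after 14 days in postmenopausal women: "25% of tumors exhibited complete cell cycle arrest (secondary objective) with giredestrant (GDC-9545) versus 5% with anastrozole". The same section reports 51% for giredestrant in the phase I window study.

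**The concern.** A Wald test divides the estimated log odds ratio by its standard error. When one arm has no responders, the maximum-likelihood estimate runs off to infinity and its standard error grows much faster, so the ratio goes to zero and the p-value to 1. The planned test would then be least able to detect a difference when the observed contrast is at its greatest, and the odds-ratio interval would be unusable.

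A low tamoxifen rate is plausible. Besides the 5% for anastrozole, Protocol 1.4 reports weaker two-week Ki67 suppression with tamoxifen than with anastrozole (59% against 76%). If a zero cell occurred, the team would have to choose another test after seeing the result of an open-label trial.

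**Working it through.** **Inputs.** SAP 1.6 gives 46 randomised per arm and 10% dropout: 46 × 0.90 = 41.4, taken as 41 evaluable. Alpha is 0.05 two-sided (SAP 4.4.2). CCCA rates of 25% and 51% for giredestrant and 5% for anastrozole are from Protocol 1.5.1. Control rates of 1%, 2%, 8% and 10% are assumptions.

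**Plan's own figure.** The plan states no rate, power or sample size for CCCA. The primary sample size reproduces: 34 per arm for 20 points with SD 29; then 34/0.86 = 39.5 and 39.5/0.90 = 43.9, so 44 against the stated 46. That small difference is not at issue. The figure is used only to reach 41.

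**1. The zero cell.** For *a* of *n* giredestrant and *c* of *n* tamoxifen responders, log OR = ln[a(n−c) / (c(n−a))] and SE = √[1/a + 1/(n−a) + 1/c + 1/(n−c)]. At c = 0 both are undefined, and software stops at an arbitrary iteration. For 10/41 against 0/41 one fit gave 22.43 with SE 12,410, so z = 0.0018 and p = 0.999. Another stopping rule gave 19.07 with SE 3,807 and p = 0.996.

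| Giredestrant vs 0/41 | Wald p | Fisher p | Score p |
|---|---|---|---|
| 10/41 | 0.996–0.999 | 0.001 | 0.0007 |
| 21/41 | 0.996–0.998 | 3 × 10⁻⁸ | 1 × 10⁻⁷ |
| 33/41 | 0.996 | 2 × 10⁻¹⁵ | 1 × 10⁻¹³ |

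**2. How likely it is.** P(no tamoxifen responder) = (1−p)ⁿ.

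| Control rate | n = 41 | n = 46 |
|---|---|---|
| 1% (assumed) | 66% | 63% |
| 2% (assumed) | 44% | 40% |
| 5% (anastrozole figure) | 12% | 9% |
| 10% (assumed) | 1.3% | 0.8% |

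If mITT exclusions cut the arm to 34, the 5% row becomes 0.95³⁴ = 17%.

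**3. Exact power, 41 per arm.** Binomial probabilities are summed over all tables with p ≤ 0.05. Wald is counted as non-significant when a cell is zero.

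| Giredestrant / control | Wald | Fisher | Score |
|---|---|---|---|
| 25% / 1% | 28% | 91% | 98% |
| 25% / 2% | 44% | 86% | 94% |
| 25% / 5% | 58% | 66% | 77% |
| 25% / 8% | 48% | 46% | 57% |
| 25% / 10% | 38% | 35% | 45% |
| 51% / 2% | 56% | 100% | 100% |
| 51% / 5% | 88% | 99.9% | 100% |

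Between 5% and 1% control, with giredestrant at 25%, Wald power falls as the true difference grows.

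**4. Where the gap arises.** At 25% against 5%, P(at least one control responder) = 1 − 0.122 = 0.878. Given that, power is 66% for Wald and 62% for Fisher. Wald overall is therefore 0.878 × 0.66 = 0.58. Fisher has 0.878 × 0.62 = 0.54 from the same tables, and the remaining 0.66 − 0.54 = 0.12 comes from tables with no control responder. Given exactly one or two control responders, power is Wald 78%, Fisher 78%, score 90%.

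**5. Size.** With equal true rates between 1% and 10%, Fisher's size is at most 1.8% and the score test's at most 5.9%, the latter when both rates are 10%.

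**The case against.** The strongest reply is that the near-zero control rate is assumed. The 5% is for anastrozole, in postmenopausal women with baseline Ki67 of 5% or more, from preliminary data on 83 patients. EMPRESS enrols premenopausal women with Ki67 of 10% or more. CCCA rates also transfer poorly between trials: Protocol 1.5.1 itself reports 51% and 25% for giredestrant. This stands. At 5% a zero cell is a minority outcome, and at 10% or more the problem practically vanishes.

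A reader might infer that Wald is also badly underpowered with one or two control responders. The calculations do not support that: it matches Fisher there, and 10/41 against 2/41 gives Wald p=0.023 and Fisher p=0.026.

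A reader might also infer that any replacement is free of cost. It is not. Fisher has less power than Wald from a control rate of about 8%, and the score test can slightly exceed nominal size.

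Finally, the report would not be silent in the zero-cell case. The planned Clopper-Pearson intervals would be 0 to 8.6% for 0/41 and 12.4% to 40.3% for 10/41, which do not overlap. Post-treatment Ki67 is also compared by Wilcoxon test, which separation does not affect. SAP 4.1 calls the study exploratory, and CCCA carries no power claim. These points limit the consequence, but they do not make the planned p-value or odds-ratio interval valid.

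**Conclusion.** The point holds as a gap in the specification: the planned between-arm test for CCCA fails if the tamoxifen arm has no responders, and nothing in either document says what to do then. The algebra is certain. How often it would matter depends on an unknown tamoxifen rate: 12% of trials at 5%, 44% at 2%, 66% at 1% and about 1% at 10%, assuming 41 evaluable per arm.

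The documents do not show that the tamoxifen rate is near zero, and the defect is confined to the zero cell. It does not touch the primary analysis or its sample size. It is worth correcting because the case is realistic, the error can be gross, and a choice made after the data are seen would be open to challenge.

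**What to change.** In SAP 4.4.2 and Protocol 8.7, prespecify one between-arm test for CCCA:

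- **Test:** the score (Pearson chi-square) test, two-sided at 0.05.
- **Estimate:** the risk difference with its Miettinen-Nurminen 95% CI. This interval is also score-based, so it should agree with the test except in borderline tables.
- **Odds ratio, if wanted:** Firth-penalised logistic regression with profile-likelihood limits.

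Keep the Clopper-Pearson intervals for each arm. If only the SAP is changed, record the change in SAP section 6. Settle the wording before database lock.

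The cost is a few sentences and a few program lines, with no new data. The statistical cost is a size of up to about 5.9% when both rates are 10%. If strict control is preferred, Fisher's exact test gives it, at the price of less power than Wald when the control rate is about 8% or more. Name one test only, so that the choice is not left until the counts are known.
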